Subjects meeting enrollment criteria will be entered into this clinical trial. Following enrollment, subjects will be stratified by gestational age and by chronologic age as follows: 1) \leq 27 weeks 6 days gestational age at birth and \leq 30 days chronologic age at study enrollment; 2) \leq 27 weeks 6 days gestational age at birth and $>$ 30 days chronologic age at study enrollment; 3) \geq 28 weeks 0 days gestational age at birth and \leq 30 days chronologic age at study enrollment; 4) \geq 28 weeks 0 days gestational age at birth and $>$ 30 days chronologic age at study enrollment. The total sample size across these four cohorts is 32 subjects. Subjects in each cohort with inadequate pharmacokinetic data for analysis (e.g., due to dropping out of the study before PK assessments are performed, or blood sampling obtained but is inadequate for analysis) may be replaced and will not count toward the total of 32 subjects. Additionally, enrollment of an additional 2-3 subjects may be allowed for operational reasons.

A full pharmacokinetic profile will be obtained following at least one of the ganciclovir doses received after study enrollment. The PK samples will be obtained after the subject has received study assessment dose 3, 4, 5, 6, 7, or 8 of intravenous ganciclovir. Typically, ganciclovir is administered twice per day in these infants for a duration in excess of 10 days. Specimens will be shipped for processing at that time. The pharmacokinetic data will then be provided to the study site, including the AUC and CL values for information purposes.

[figure not shown]
Dose and duration of intravenous ganciclovir therapy is at the discretion of the treating physician and will not be dictated by the research protocol. Both whole blood for CMV PCR and urine for CMV detection will be obtained once in each study period as long as the subject is receiving intravenous ganciclovir therapy. These specimens will be used to determine viral load and ganciclovir resistance. Since ganciclovir is a renally

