3 OBJECTIVES

3.1 Study Objectives

Primary:

- To define the pharmacokinetics of ganciclovir in premature (< 32 weeks gestational age at birth) infants

Secondary:

- To assess changes in quantitative viral DNA in whole blood as a function of ganciclovir pharmacokinetics
- To assess clearance of CMV in urine as a function of ganciclovir pharmacokinetics

Exploratory:

- To assess development of neutropenia as a function of ganciclovir pharmacokinetics
- To determine the potential for the development of resistance to ganciclovir as a function of pharmacokinetics, dose, age, and duration of therapy

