3.2.2 Secondary Outcome Measures

Secondary Endpoints:

- Plasma pharmacokinetics parameters for ganciclovir, including maximum serum concentration (Cmax), half-life (T1/2), CL, and Vd
- Correlation of ganciclovir plasma concentrations with CMV whole blood viral load
- Correlation of ganciclovir plasma concentrations with clearance of CMV in urine

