Both whole blood for CMV PCR and urine for CMV assessment will be obtained serially through Study Assessment Period 7 as long as the subject is receiving intravenous ganciclovir therapy (that is, until the ganciclovir is permanently discontinued). These specimens will be used to determine viral load and, as indicated, ganciclovir resistance. At each sample collection time, urine will be split into two aliquots. These aliquots will be available for CMV detection as appropriate, based upon whole blood viral loads. Specimens will then be available for subsequent testing for ganciclovir resistance in the UAB Virology Resistance Laboratory. Since ganciclovir is a renally excreted drug, serum creatinine will be drawn for the research protocol on the day that the ganciclovir pharmacokinetic specimens are obtained in order to calculate creatinine clearance using a method such as the modified Schwartz formula, and thus correlate ganciclovir clearance with renal function. Otherwise, data from hematology assessments (WBC count and differential, hemoglobin, platelet count) and from chemistry labs (serum creatinine, ALT, and AST) will be recorded on the study case report forms each study assessment period if they are being obtained for clinical reasons, but will not be drawn only for the purposes of the study. Ganciclovir dosing information (mg/dose, dosing interval, and subject weight) will be recorded on the day of the pharmacokinetic blood draws. Once a subject is successfully enrolled into the study the ganciclovir dosing information (mg/dose and dosing interval) will be recorded from the start of clinical treatment of ganciclovir until date of enrollment. After enrollment ganciclovir dosing information (mg/dose and dosing interval) will be captured from Study Assessment Period 1 through the Study Assessment Period 7; as long as the subject is receiving intravenous ganciclovir therapy.

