7.3 Follow-up

7.3.1. Period 2 (Study Assessment Day 4 through Study Assessment Day 10)

Documentation of receipt of PRBC transfusion(s) will be provided on an eCRF. If the study subject has NOT received ≥ 10 PRBC transfusions (see Section 9.3.1), proceed with required assessments.

Required assessments [following confirmation that subject is still receiving ganciclovir (e.g., that the ganciclovir has not been permanently discontinued)]: 1) virology blood

specimens for CMV viral load (required amount of whole blood for CMV PCR is 0.5 mL); 2) CMV detection from noninvasive urine specimen (if obtainable); 3) ganciclovir dosing information (mg/dose, dosing interval, subject weight).

Optional assessments (if being drawn for clinical reasons; any laboratory value obtained during the window will suffice, with an effort being made to capture the most abnormal value): 1) hematology labs (WBC with differential, hemoglobin, platelet count); 2) chemistry labs (AST, ALT); 3) serum creatinine.

Study Assessments (as described)	Optional Assessments*
Virology blood specimens for CMV viral load	Hematology labs (WBC with differential, hemoglobin, platelet count)
If obtainable, CMV detection from noninvasive urine specimen (e.g., bagged, from indwelling foley catheter, excess clinical specimen, etc.)	Chemistry labs (AST, ALT)
Ganciclovir dosing information (mg/dose, dosing interval, subject weight)	Serum creatinine

* If being drawn for clinical reasons; any laboratory value obtained during the window will suffice, with an effort being made to capture the most abnormal value

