8.2.1.1. CMV Viral Load/Resistance Testing

[figure not shown]
Assessment of CMV viral load in whole blood will be conducted at the UAB Central Laboratory. The required amount of whole blood for CMV PCR is 0.5 mL. Whole blood will be collected at each study visit from Period 1 through Period 5. Whole blood will also be collected at the Period 6 study visit if the

subject weighs at least 600 grams, and at the Period 7 study visit if the subject weighs at least 650 grams.

Urine collection by noninvasive mechanism (e.g., bagged, indwelling foley catheter, excess clinical specimen, etc.) will be attempted at each study visit. If urine is obtainable, it will be frozen and sent to the UAB Central Laboratory for processing. If an attempt to obtain urine for CMV detection is unsuccessful, study staff will document the failed attempt on a source document. All specimens collected will be sent to the UAB Central Laboratory.

Viral detection assays will be performed in the UAB Central Laboratory. These assays and tests are in clinical and research use already in the Central Laboratory. The detection of CMV DNA will be performed using the CMV two primer Taqman assay already employed regularly in our laboratory. The detection limit of our real-time PCR assay, as determined by the sensitivity titration analysis, is 10 genomic equivalents per reaction. The results of 10 different runs on different days are shown in the Table below. Regression analysis shows a very high correlation coefficient (0.9996) for the 6 log concentration range (see Figure below).

genome equivalents	log(10)	# +/10	ct(mean)	std
1000000	6	10/10	18.362	0.085609
100000	5	10/10	21.476	0.155863
10000	4	10/10	24.855	0.187157
1000	3	10/10	28.321	0.305449
100	2	10/10	31.869	0.2283
10	1	10/10	35.283	0.606045

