APPENDIX G**STUDY CLOSURE CHECKLIST FOR DATABASE LOCK**

Task	Completed	Signed off	Date	Role
	Yes/No			
All queries resolved				
All site data 100% monitored at site				
All expected specimens received for PK analysis				
All expected specimens received for PBMC analysis				
All expected specimens received for virology analysis				
All PK analysis complete				
All PBMC analysis completed				
All virology specimens analyzed				
All culture specimens complete				
All required sequencing data completed				
PD contacts COTR to request database lock				

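### Protocol Section 4 ties urine CMV testing to the blood viral load, contrary to the schedule, and so puts the urine-clearance endpoint at risk of selection bias

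*Protocol*

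**What the plan says.** Urine clearance is both a secondary objective (Protocol Section 3.1: "To assess clearance of CMV in urine as a function of ganciclovir pharmacokinetics") and a secondary endpoint (Section 3.2.2: "Correlation of ganciclovir plasma concentrations with clearance of CMV in urine").

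On which urine specimens are tested, the documents say two things.

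- **Conditional.** Section 4 has urine split into two aliquots at each collection and continues: "These aliquots will be available for CMV detection as appropriate, based upon whole blood viral loads". No cut-off is given. Nothing says whether a high or a low blood result triggers testing, or how untested urine enters the analysis.
- **Unconditional, if urine can be had.** Section 7.3.1 (Period 2) lists "2) CMV detection from noninvasive urine specimen (if obtainable" among the required assessments, and Periods 3, 5, 6 and 7 repeat this. The Protocol Summary says "Both whole blood for CMV PCR and urine for CMV detection will be obtained once in each study period", for as long as intravenous ganciclovir continues. Section 8.2.1.1 says "If urine is obtainable, it will be frozen and sent to the UAB Central Laboratory for processing". Protocol Appendix A and SAP Section 6, Table 1 mark urine CMV detection in all seven periods. The lock checklist in SAP Appendix G has the item "All virology specimens analyzed", with no exception for urine.

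Protocol Section 11.4 and SAP Appendix B analyse urine CMV against plasma concentration with GEE for repeated binary data. Neither mentions urine left untested because of the blood result.

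**The concern.** Blood viral load is itself a response variable. Section 11.4 relates it to the pharmacokinetic parameters and provides for a group with undetected virus. If it decides which urines are tested, the urine data become a sample selected on something that exposure may influence and that may track urinary shedding. Unweighted GEE is in general valid only when missingness is unrelated to the outcome given the covariates in the model. Selection of this kind can distort the proportion cleared and its relation to exposure, and that relation is the secondary endpoint.

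There is also an operational problem: two laboratories, or one laboratory at two times, could apply the text differently and both claim to follow the protocol.

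**Working it through.** The documents give no figure for the urine endpoint; the power calculation in Section 11.2 concerns AUC12 only. There is nothing to reproduce, so the check is of the text, followed by an illustration.

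**1. Does the condition cover detection or only resistance testing?** It covers detection. Earlier in the same paragraph of Section 4, resistance testing has its own qualifier, that it is done as indicated. The sentence after the quoted one then makes specimens available for later resistance testing.

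**2. How does this compare with the other sections?**

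| Place | What is asked of urine | Blood viral load condition? |
|---|---|---|
| Protocol 4 | Detection where appropriate | Yes, no threshold |
| Protocol 7.3.1, 7.3.2, 7.3.4, 7.3.5, 7.4.1 (Periods 2, 3, 5, 6, 7) | Detection, a required assessment if obtainable | No |
| Protocol 7.2.1, 7.3.3 (Periods 1, 4) | Collection for detection, if obtainable | No |
| Protocol 8.2.1.1 | Collection attempted; urine obtained is frozen and sent | No |
| Protocol Appendix A; SAP Section 6, Table 1 | Detection in all seven periods | No |
| SAP Appendix G | All virology specimens analysed before lock | No |

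**3. Can the condition always be applied?** No. Blood for viral load is not drawn below 600 g in Period 6 or below 650 g in Period 7. Study draws may be deferred, and unevaluable specimens are not repeated (Section 5.3.2). Non-invasively collected urine can then exist with no blood result to decide its testing.

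**4. How much could selection matter?** Every input here is assumed. The simulation had 60,000 infants and 7 periods.

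- Latent log10 viral loads started at 3.5 (blood) and 4.0 (urine). Both fell by 0.25 per period and by 0.4 per SD of ganciclovir AUC.
- Between-infant SD was 1.0 and within-infant SD 0.5, with blood-urine correlation rho at both levels.
- Blood was positive at 2.5 or above (about 58% of samples). Urine was cleared below 3.0.
- The fitted model was logistic regression of clearance on AUC and period, pooled over visits. This equals the GEE point estimate under an independence working correlation; the plan names no working correlation.

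Each cell shows the percentage cleared, then the log-odds slope per SD of AUC.

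| rho | All urine tested | Only if blood positive | Only if blood negative | Tested if blood positive, rest counted as cleared |
|---|---|---|---|---|
| 0 | 42.2; 0.585 | 35.4; 0.574 | 51.5; 0.599 | 62.7; 0.725 |
| 0.5 | 42.2; 0.587 | 24.1; 0.465 | 66.9; 0.417 | 56.3; 0.655 |
| 0.9 | 42.2; 0.601 | 10.5; 0.366 | 85.5; 0.333 | 48.3; 0.611 |

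At rho = 0 the percentages still move, because AUC and time drive both fluids. With AUC given no effect on either fluid and rho = 0, clearance within a single period was 41.1% in all samples and 41.4% in the blood-positive ones, so there was no bias.

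The error in clearance changes sign with the testing rule. The slope is weakened under either selective rule once rho is above zero, and strengthened if untested urine counts as cleared.

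**5. How many assays would full testing need?** 32 × 7 = 224 at one urine per period. With the three extra infants that Section 4 allows, 35 × 7 = 245. Replaced infants would add to this. Section 2.1 puts typical total antiviral treatment at two to four weeks. If study assessment starts with treatment, Day 14 falls in Period 3 and Day 28 in Period 5, giving about 32 × 3 = 96 to 32 × 5 = 160.

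**The case against.** The strongest reply is that one loosely worded sentence stands against the rest of the plan. It says only that aliquots will be available where appropriate, and sites and laboratory may in practice test everything, as the schedules imply. Bias then needs three things: some obtained urine goes untested, blood and urine results are associated, and the analysis ignores the selection. The documents establish none of the first two. This stands, and it is why the point is a contradiction that creates a risk rather than a demonstrated bias.

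A reader might go further and infer that the missing results sit in the best responders, or that untested urine will be counted as clear. Neither follows. Section 4 does not say that low blood results are the ones skipped; urine could as well be tested only once blood is negative. No passage assigns untested urine a status. Nor can the share of visits affected be calculated, because the documents give neither the frequency of undetectable blood nor that of positive urine at such visits.

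It would also be too strong to say that every other section demands a urine result. Periods 1 and 4 ask for collection, and Section 8.2.1.1 for attempted collection and shipment. The lock checklist does not name urine separately. These places are silent on the condition; the direct conflict is with the required-detection wording for Periods 2, 3, 5, 6 and 7 and with the schedules.

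**Conclusion.** The protocol contradicts itself on whether every urine obtained is tested for CMV, and one of the two readings selects the data for a secondary endpoint on another response variable. The analysis plan makes no allowance for that. The contradiction and the missing provision rest on the text alone.

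The bias is a possibility whose size and direction depend on a rule that the documents do not state. The simulation shows that it could be large at moderate blood-urine correlation, but its inputs are assumptions and its figures are not estimates for this study. The primary endpoint, AUC12, is not affected. The matter deserves correction because the wording is easily put right and the specimens are already being collected.

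**What to change.** In Protocol Section 4, remove the part of the quoted sentence that makes detection depend on judgement and on the blood viral load. State instead that every urine specimen obtained is tested for CMV, in line with Section 7 and Appendix A. Leave the existing wording on resistance testing unchanged: a viral load condition there would be a new rule and would introduce selection into an exploratory endpoint.

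The cost is a wording change and laboratory assays on urine already collected and shipped: at most 7 per infant, within the totals worked out above, and fewer where treatment is short or urine is not obtained. It adds no procedure for the infants.

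If conditional testing is really intended, the protocol and SAP should state the threshold, its direction, what happens when there is no blood result, and how untested urine is counted. They should also specify an analysis that allows for the selection, with sensitivity analyses. One option is GEE weighted by the probability of testing, which needs some urine tested at every blood level; another is a joint blood-urine model. This is more work than testing every specimen and rests on more assumptions.

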5 STUDY ENROLLMENT AND WITHDRAWAL

Male and female premature infants < 32 weeks gestation of any ethnicity who are being treated with intravenous ganciclovir for proven [e.g., culture- or polymerase chain reaction (PCR)-confirmed] CMV infections are eligible for enrollment. Participating clinical sites will identify potential study subjects. Patients meeting study eligibility criteria may be offered enrollment into the trial. Informed consent signed by study subject's parent(s) or guardian(s) must be obtained prior to study enrollment. Site investigators are all clinicians and also care providers for the neonatologists at their respective institutions, and therefore have direct access to the study population. The study population will be drawn from the in-hospital setting. Potential subjects will be identified by the site investigators and the study coordinators.

5.1 Subject Inclusion Criteria

1. Signed informed consent from parent(s) or legal guardian(s)
2. Confirmation of CMV infection from urine, blood, or saliva by culture, shell vial, or PCR tests (local lab)
3. Receiving intravenous ganciclovir, prescribed by the patient's physician and anticipated to receive at least 3 more doses after consenting
4. < 32 weeks gestational age at birth
5. ≥ 500 grams at study enrollment

5.2 Subject Exclusion Criteria

1. Imminent demise
2. Current receipt of valganciclovir or foscarnet
3. Receiving breast milk from a mother who is being treated with ganciclovir or valganciclovir
4. Current receipt of other investigational drugs
5. Major congenital anomaly that in the site investigator's opinion may impact drug metabolism or the patient's volume of distribution

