2 BACKGROUND INFORMATION AND SCIENTIFIC RATIONALE

2.1 Background Information

The natural history of congenitally acquired CMV infection is well described.¹⁻⁷ In contrast, outcomes of perinatally and postnatally acquired CMV infections are less well characterized. It is generally agreed that postnatal acquisition of CMV in term infants does not lead to symptomatology or disease.⁸ In preterm infants, initial case reports suggested that peri- and postnatally acquired CMV infections could produce severe disease.⁹⁻¹⁴ Larger series and case-controlled trials more recently suggest that symptomatic disease in preterm babies is less common than asymptomatic infection, and long-term sequelae are rare.¹⁵⁻¹⁹ Nevertheless, severe disseminated CMV disease can occur in premature infants, including life-threatening pneumonitis, hepatitis, and thrombocytopenia.²⁰ Antiviral therapy in such patients is frequently used, albeit without either controlled data to demonstrate benefit or knowledge of proper dosing regimens.¹² In patients with symptomatic congenital CMV disease, six weeks of intravenous ganciclovir improves hearing outcomes in early childhood,²¹ and may benefit neurodevelopmental outcomes as well.²² In premature babies with visceral disease from postnatally acquired CMV, the goal of antiviral therapy is different; namely, it is to treat the end-organ disease, which is occurring at that time, rather than to prevent or improve long-term sequelae. Without efficacy data, the duration of treatment is variable, but anecdotal experience suggests that it generally is in the range of two to four weeks of total antiviral therapy. Approximately two-thirds of treated neonates receiving six weeks of intravenous ganciclovir develop Grade 3 or 4 neutropenia (utilizing the DAIDS Toxicity Tables) during therapy.²¹

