5.3.3 Reasons for Withdrawal

The criteria for discontinuations during the study include:

- Study subject (parent/legal guardian) wishes to withdraw
- Non-compliance with study procedures
- Trial termination (by UAB, , FDA, DMID, NIAID, NIH, or agreement of all investigators)
- Any other reason which, in the opinion of the investigator, precludes the study subject's participation in the study. The principal investigator must call the Protocol Chair prior to discontinuing a study subject for this reason.

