8.1 Clinical Evaluations

8.1.1. Baseline Demographics

To characterize the study subjects, information will be recorded at the baseline study visit (Period 1) following the obtaining of informed consent. Data collected will include basic demographics and birth history (date of birth; gender; race; ethnicity; birth weight; weight at enrollment; length in centimeters at enrollment; reason ganciclovir is being administered, gestational age at birth; ganciclovir dose and dosing frequency at time of enrollment; detailed ganciclovir dose and dosing frequency since ganciclovir therapy was initiated; manufacturer of the ganciclovir lot utilized at the treating facility; and date ganciclovir therapy was initiated).

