A 95% confidence interval will be constructed to evaluate the mean changes in the log of the viral load between baseline (day 1) and weeks 1, 2, 3, 4, 5, and 6. Area under the curve will be calculated for each subject's CMV viral load measurement utilizing the trapezoidal rule. These AUCs will be calculated over the entire course of drug administration. Spearman's correlations will be given for each AUC estimation and also for the AUC after baseline viral load (VL) adjustment. Analysis of variance will be used to investigate whether grouping AUCs into groups (undetected, 100-1000, 1000-10000 and ≥ 10000) would indicate any PD relationships. In addition, changes in CMV viral load from baseline over time (weeks 1 through 6) will be correlated with PK parameters. These data will provide the framework for all PD analyses, where ganciclovir exposures variables will be correlated with the response variables using linear or maximum effect PD models.

Secondary analyses: To investigate the association of secondary outcomes namely, neutropenia, CMV in urine, viral load and resistance to ganciclovir, with plasma concentration, we will utilize inference methods based on Generalized Estimating Equations (GEE) which models repeated binary data. As in the primary analysis, GEE will enable us to compare groups, investigate changes of outcomes over time, and adjust for any covariates.

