- 4.3.4.3 If the PD or designee confirms the need to unlock the eCRF page, s/he will administratively unlock specific data field or form
- 4.3.4.4 Following updating the data field(s) the user will lock the eCRF again.
- 4.3.4.5 Changes will be tracked electronically in the database to provide a 'paper trail' for changes.
- 4.3.4.6 Information will be retained in the database noting who made the change, what the change was and when the change occurred.
- 4.3.5 Sites will have the ability to print the locked eCRF.
- 4.3.6 'Same data fields' between eCRFs will be linked/ autopopulated to assure no discrepancy occurs.
- 4.3.7 Adverse event form
 - 4.3.7.1 If an AE is reported it may be locked if the event is ongoing. Each time eCRFs are completed, the end user will be notified that ongoing AEs are present.
 - 4.3.7.2 The AE form can be opened and updated. When an event is resolved or resolved with sequelae, the form cannot be opened by the site without requesting permission from the CSA or designee.
- 4.3.8 Unscheduled eCRF: forms that may be used at any time as needed during the course of the study
 - 4.3.8.1 Additional comments page
 - 4.3.8.2 Protocol deviation (refer to section 10.6)
 - 4.3.8.3 PBRC transfusion page
 - 4.3.8.4 Adverse event page
 - 4.3.8.5 Protocol completion/termination (for use when subject has not completed last dose of study drug). Following completion of this form, all forms after this visit/phase will not be accessible.
- 4.3.9 Site wide forms: forms that are used that are not subject-specific or contain multiple subject data.
 - 4.3.9.1 Protocol deviation (refer to section 10.6)
 - 4.3.9.2 Additional comments page
 - 4.3.9.3 Specimen shipping form (virology and pharmacokinetic)
- 4.3.10 Subsequent forms: select forms that must be completed before proceeding
 - 4.3.10.1 Following administration of last dose of assessment dose drug, all CRFs will be inaccessible until completion of Protocol Termination/Completion found in the Subsequent forms menu.
 - 4.3.10.2 Completion of this form makes all forms accessible

5. CRF Query Design and Functionality

- 5.1. Purpose of Query Design and Functionality
 - 5.1.1 The purpose of the query system is to track all requested changes to the CRF system
 - 5.1.2 The query system is managed/tracked in three ways:
 - 5.1.2.1 for monitor queries for issues identified during interim monitor visits

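### Drugs added to continuing ganciclovir are not visibly recorded after entry, so the secondary and exploratory PD analyses cannot separate their effects; the primary AUC12 endpoint is unaffected

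*Protocol*

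**What the plan says.** **Entry.** Protocol 5.2 excludes infants with "Current receipt of valganciclovir or foscarnet" and with "Current receipt of other investigational drugs". Both criteria describe the state at enrolment. No section extends them to the weeks that follow.

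**Staying in.** Protocol section 4, sections 7.3.1 to 7.4.1 and Appendix A (note a) make continued sampling depend on one thing: that intravenous ganciclovir has not been permanently stopped. Ten or more transfusions end the study blood draws (9.3.1). The withdrawal reasons in 5.3.3 do not mention starting another drug. The nearest is the general clause, "Any other reason which, in the opinion of the investigator, precludes the study subject's participation in the study".

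**Treatments recorded.** At baseline, 8.1.1 asks for "detailed ganciclovir dose and dosing frequency since ganciclovir therapy was initiated". In later periods the schedule asks for ganciclovir dosing and the number of red-cell transfusions. The SAP schedule (CRF Workflow, Table 1) is the same. SAP Appendix C, 4.3.8, under "Unscheduled eCRF: forms that may be used at any time as needed during the course of the study", lists pages for comments, deviations, transfusions, adverse events and completion. Adverse events are limited to those tied to blood draws or reportable to the IRB (Protocol section 9).

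**Analysis.** Protocol 11.4 and SAP Appendix B plan 95% intervals for mean change in log viral load, Spearman correlations for viral-load AUC, correlation of viral-load change with PK parameters, and GEE models "To investigate the association of secondary outcomes namely, neutropenia, CMV in urine, viral load and resistance to ganciclovir, with plasma concentration". Covariate adjustment is allowed. Those named are gestational age, weight and renal function.

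**The concern.** The entry criterion shows that the sponsor regards other anti-CMV drugs as able to disturb the question. The same drugs can be added a week later without any visible trace in the data. Immune globulin and G-CSF appear in neither document.

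Two errors would follow if such treatment occurs:

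- **Mean viral-load change.** This is a single-group estimate, so the extra decline from an added agent is counted as decline under ganciclovir.
- **Exposure-response and exposure-neutropenia relations.** Here the usual error runs the other way. An added antiviral tends to go to infants who respond poorly, and G-CSF to infants who become neutropenic. Treatment that follows the outcome flattens its relation with ganciclovir exposure.

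Neutropenia is not rare in the setting the protocol cites: "Approximately two-thirds of treated neonates receiving six weeks of intravenous ganciclovir develop Grade 3 or 4 neutropenia" (2.1). The endpoints at stake are the two secondary PD correlations (3.2.2) and, among the exploratory ones, chiefly neutropenia (3.2.3). With 32 infants, a reader could not tell a weak relation from a masked one.

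**Working it through.** The documents give no figure for co-treatment, so there is none to reproduce. All inputs below are assumptions, except n = 32.

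**Added antiviral.** Let z be standardised exposure.
- Weekly log10 decline = 0.3 + 0.15z + error (SD 0.2).
- An infant qualifies for an added drug if the measured week-2 decline (measurement SD 0.3) is below 0.3. The drug adds 0.5 log10 per week for two weeks, so 1.0 log10 by week 4.

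Without added drug:
- Mean week-4 decline = 4 × 0.3 = 1.20; slope on z = 4 × 0.15 = 0.60.
- Pearson correlation = 0.15/√(0.15² + 0.2²) = 0.15/0.25 = 0.60; Spearman = (6/π) × arcsin(0.60/2) = 0.58.

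Share that qualifies: week-2 decline has mean 0.6 and SD √(2² × 0.0625 + 0.09) = 0.583, so the share is Φ((0.3 − 0.6)/0.583) = Φ(−0.51) = 0.30. The 8% and 15% cases therefore treat about 0.08/0.30 = 26% and 0.15/0.30 = 49% of those who qualify.

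Mean with added drug = 1.20 + share × 1.0. Slope and Spearman are simulated (400,000 infants, week-4 decline without measurement error):

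| Share given added drug | Mean decline (log10) | Slope | Spearman |
|---|---|---|---|
| 0% | 1.20 | 0.60 | 0.58 |
| 8% | 1.28 | 0.55 | 0.56 |
| 15% | 1.35 | 0.51 | 0.54 |
| 30% | 1.50 | 0.42 | 0.51 |

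The slope falls by about 8%, 15% and 30%. Spearman, the statistic that the plan names, falls by about 4%, 7% and 12%, because the added drug also narrows the spread of outcomes. The standard error of the slope at n = 32 is about 4 × 0.2/√32 = 0.14, so the slope shifts at 8% (0.05) and 15% (0.09) are within one standard error.

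**Harsher assumptions at n = 32** (20,000 runs, true correlation −0.5 between exposure and viral-load change). If 10% to 30% of infants, chosen as the worst responders, get a further drop of 1 to 2 SD, mean Spearman moves from −0.47 to between −0.45 and −0.17. The mean change is overstated by 3/32 × 1 = 0.09 SD up to 10/32 × 2 = 0.63 SD.

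**G-CSF.** Four periods, logit of neutropenia = −1.2 + 0.8z + u, with u standard normal. After a first neutropenic period, G-CSF multiplies later odds by 0.2. The pooled odds ratio per SD of exposure is 1.98 with none, and 1.89, 1.82 and 1.70 when 25%, 50% and 100% of affected infants get it. The largest change is ln(1.98/1.70) = 0.15, against a standard error of at least about 0.22 at n = 32. For ever having neutropenia the odds ratio barely moves (2.31 against 2.28), since onset precedes G-CSF in this model.

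**The case against.** Much of the case on the other side stands.

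- **Few infants may be affected.** A full switch from intravenous ganciclovir to another drug ends sampling, so only add-on treatment matters. Protocol 2.1 puts usual treatment at two to four weeks, so a week-4 effect concerns the longer-treated infants. How often anything is added is unknown.
- **The effects are modest.** On the planned Spearman correlation the first model gives a loss of at most 12%. Recording the most abnormal value in each period protects the period in which neutropenia starts, though not later periods in the GEE.
- **Not every form is visible.** The SAP keeps annotated CRFs and the data dictionary available on request, and Appendix D is not in the reviewed copy. What can be said is that no visible schedule or form list holds such a record.

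A reader might infer more than the documents support:

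- *The information is lost for good.* It is not. All subjects are inpatients (7.6), hospital and pharmacy records are source documents (section 12), and records are kept for at least two years (15.5). Later abstraction is possible; prospective capture is more reliable.
- *Another drug may have driven resistance.* Nothing in the documents supports this, and ganciclovir history is recorded from the start of therapy.
- *Added drugs could reverse the exposure-response relation.* In the n = 32 simulation that happens only if they go to low-exposure infants. Section 4 returns AUC and clearance to the site, but speaks only of dose adjustment.

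**Conclusion.** The gap is real and limited: a cheap improvement for the secondary and exploratory PD endpoints. The primary endpoint, AUC12, is calculated from ganciclovir concentrations around one dose in the first five study days, and response to other drugs does not enter it.

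If drugs are added, the mean viral-load decline under ganciclovir is overstated by the share treated times the effect of the added drug: 0.08 to 0.30 log10 in the main illustration. The exposure relations are modestly attenuated when the addition follows poor response or neutropenia. These sizes rest on assumed usage, drug effect and prescribing pattern. If nothing is added, there is no bias, but without a record the report cannot show that. Adjustment for covariates does not close the gap while co-treatment is not among the data collected.

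**What to change.** **Data.** Add one eCRF page per period to Protocol Appendix A and the SAP schedule, abstracted from the chart: name and start and stop dates of any other anti-CMV agent, immune globulin or G-CSF, including anti-CMV drugs given before enrolment. If an existing form already holds this, cite it in both schedules.

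**Analysis** (Protocol 11.4 and SAP Appendix B).
1. The ganciclovir PK/PD analyses of viral load, urine CMV and resistance use results up to the start of another anti-CMV agent, with all data as a sensitivity analysis. Report how many infants are affected.
2. Keep those infants' earlier viral loads, for instance in the repeated-measures mixed model that 11.4 already names. Simply deleting the later values leaves the better responders. In the 30% case the mean of the remaining week-4 values is 1.20 + 0.857 × 0.350/0.697 = 1.63, where 0.857 is the correlation of week-2 measured with week-4 decline (0.5/0.583), the week-4 SD is 1.0, and 0.350 and 0.697 are the normal density and retained share at the cut-off. That is further from 1.20 than the all-data 1.50.
3. Flag neutrophil counts taken on G-CSF, and exclude them in a sensitivity analysis or adjust for them. Keep the planned GEE for binary outcomes.

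**Cost.** A short form from the chart, with no extra blood or visits, and a few later values leaving the main PD model. No treatment rule is implied.
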